3.5.2 Drug and Drug Procurement

Simvastatin Description

Simvastatin is a lipid-lowering agent that is derived synthetically from a fermentation product of *Aspergillus terreus*. After oral ingestion, simvastatin, which is an inactive lactone, is hydrolyzed to the corresponding β -hydroxyacid form. This is an inhibitor of 3-hydroxy-3-methylglutaryl-coenzyme A (HMG-CoA) reductase. This enzyme catalyzes the conversion of HMG-CoA to mevalonate, which is an early and rate-limiting step in the biosynthesis of cholesterol.

Simvastatin is butanoic acid, 2,2-dimethyl-,1,2,3,7,8,8a-hexahydro-3,7-dimethyl-8-[2-(tetrahydro-4hydroxy-6-oxo-2H-pyran-2-yl)-ethyl]-1-naphthalenyl ester, [1S-[1 α ,3 α ,7 β ,8 β (2S*,4S*),-8 α β]]. The empirical formula of simvastatin is C₂₅H₃₈O₅ and its molecular weight is 418.57. Its structural formula is:

Simvastatin

Simvastatin is a white to off-white, nonhygroscopic, crystalline powder that is practically insoluble in water, and freely soluble in chloroform, methanol and ethanol. Simvastatin's inactive ingredients include: ascorbic acid, citric acid, hydroxypropyl cellulose,

hypromellose, iron oxides, lactose, magnesium stearate, microcrystalline cellulose, starch, talc, and titanium dioxide. Butylated hydroxyanisole is added as a preservative.

Marketed under the trade name ZOCOR, simvastatin is available for oral administration as 5 mg, 10 mg, 20 mg, 40 mg or 80 mg tablets. Simvastatin is commercially available but will be provided to patients in this clinical study through Penn's Investigational Drug Service.

[figure not shown]
Everolimus Description

Everolimus, an inhibitor of mTOR, is an antineoplastic agent.

The chemical name of everolimus is

(1R,9S,12S,15R,16E,18R,19R,21R,23S,24E,26E,28E,30S,32S,35R)-1,18-dihydroxy-12-[(1R)-2-[(1S,3R,4R)-4-(2-hydroxyethoxy)-3-methoxycyclohexyl]-1-methylethyl]-19,30-dimethoxy-15,17,21,23,29,35-hexamethyl-11,36-dioxo-4-azatricyclo[30.3.1.04,9]hexatriaconta-16,24,26,28-tetraene-2,3,10,14,20-pentaone.

[figure not shown]
The molecular formula is C₅₃H₈₃NO₁₄ and the molecular weight is 958.2. The structural formula is:

Everolimus is supplied as tablets for oral administration containing 2.5 mg, 5 mg, or 10 mg of everolimus together with butylated hydroxytoluene, magnesium stearate, lactose monohydrate, hypromellose, crospovidone, and lactose anhydrous as inactive ingredients.

Sirolimus Description

Sirolimus is an immunosuppressive agent. Sirolimus is a macrocyclic lactone produced by *Streptomyces hygroscopicus*. The chemical name of sirolimus (also known as rapamycin) is (3S,6R,7E,9R,10R,12R,14S,15E,17E,19E,21S,23S,26R,27R,34aS)-9,10,12,13,14,21,22,23,24,25,26,27,32,33,34,34a-hexadecahydro-9,27-dihydroxy-3-[(1R)-2-[(1S,3R,4R)-4-hydroxy-3-methoxycyclohexyl]-1-methylethyl]-10,21-dimethoxy-6,8,12,14,20,26-hexamethyl-23,27-epoxy-3H-pyrido[2,1-c][1,4]oxaazacyclohentriacontine-1,5,11,28,29 (4H,6H,31H)-pentone. Its molecular formula is C₅₁H₇₉NO₁₃ and its molecular weight is 914.2. The structural formula of sirolimus is:

Sirolimus is a white to off-white powder and is insoluble in water, but freely soluble in benzyl alcohol, chloroform, acetone, and acetonitrile.

Sirolimus is available for administration as an oral solution containing 1 mg/mL sirolimus. Sirolimus is also available as a white, triangular-shaped tablet containing 1 mg sirolimus, and as a yellow to beige triangular-shaped tablet containing 2 mg sirolimus.

The inactive ingredients in sirolimus Oral Solution are Phosal 50 PG® (phosphatidylcholine, propylene glycol, mono- and di-glycerides, ethanol, soy fatty acids, and ascorbyl palmitate) and polysorbate 80. Rapamune Oral Solution contains 1.5% - 2.5% ethanol.

The inactive ingredients in sirolimus tablets include sucrose, lactose, polyethylene glycol 8000, calcium sulfate, microcrystalline cellulose, pharmaceutical glaze, talc, titanium dioxide, magnesium stearate, povidone, poloxamer 188, polyethylene glycol 20,000, glyceryl monooleate, carnauba wax, and other ingredients. The 2 mg dosage strength also contains iron oxide yellow 10 and iron oxide brown 70.

Patients will remain on everolimus or sirolimus and continue to obtain those agents in the manner already established.

4. Study Procedures and Timeline

4.1 Study and Timeline Overview

The study will enroll up to 10 evaluable patients over 3-6 months. All study patients will be assigned to a starting dosage of 20 mg of simvastatin daily for a period of two months. If patient tolerability to the 20 mg simvastatin dosage decreases, the dose will be down-titrated to 10 mg daily. Intra-patient dose escalation strategy will be performed only for patients who tolerate simvastatin 20 mg daily and the daily dosage of simvastatin will be escalated to 40 mg daily during months 3 and 4. . Patients who are escalated to 40 mg daily who do not tolerate that dose, will be reduced back down to the previously tolerated 20 mg daily.

The patient will be given a copy of the informed consent form. Patients will be given ample time to read and discuss the consent form with the study staff. The study staff will then answer any outstanding questions asked by the patient. The patient will be offered the option of signing the consent form. Those who agree to participate will undergo the remainder of screening at visit 1.

Prior to starting study drug, pulmonary function tests and chest X-ray will be obtained. The spirometry values obtained that contain the best values for FEV1, FVC and DLCO will constitute the baseline values. Patients will be followed with serial VEGF-D levels collected at each visit over a four month period.

4.2 Study schedule of procedures

The table below summarizes the study procedures.

Table 1: Study Procedures

Event	Screen	Day 0	Day 30	Day 60	Day 90	Day 120
Visit number	1	2	3	4	5	6
Informed consent	X		-	-	-	-
History and physical	X		X	X	X	X
Chest X-ray	X					X
Blood levels of sirolimus (target range 3-20 ng/ml) or everolimus (target range of 3-20 ng/ml)	X		X	X	X	X
CBC, CPK, CMP *	X		X	X	X	X
Lipid profile**	X		X	X	X	X
VEGF-D		X	X	X	X	X
Saved serum and plasma		X	X	X	X	X
Urine pregnancy test	X	X	X	X	X	X
Spirometry (FEV1, FVC DLCO)		X		X		X

Review concomitant medications	X	X	X	X	X	X
Review adverse events			X	X	X	X
Study drug (simvastatin) management		X	X	X	X	X
SGRQ and FPI		X	X	X	X	X

*CMP to include BUN, creatinine, ALT, AST, Alk Phos, total bilirubin

**Lipid Panel to include total cholesterol, LDL, HDL and triglycerides.

4.3 Study Visits

4.3.1 Visit 1 - Screening

At the screening, the consent form will be presented to the potential patient. If the patient is competent to understand the risks, agrees to participate and provides informed consent and HIPAA release, the patient will undergo screening.

During this visit, the following will be performed:

- review the inclusion/exclusion criteria
- obtain a urine pregnancy test (for women of childbearing potential)
- review current medications
- review medical history and conduct a physical examination
- obtain clinical labs including: CBC, CPK, Complete Metabolic Panel (CMP), lipid panel, and sirolimus or everolimus drug level
- obtain a chest x-ray

4.3.2 Visit 2 - Day 0 (≤ 14 days of Visit 1)

After review of screening tests and confirmation the patient continues to meet eligibility criteria, the patient will return to the clinic where the following will be performed:

- obtain a urine pregnancy test (for women of childbearing potential)
- review current medications
- obtain blood for VEGF-D measurement and, if the patient has consented obtain an additional sample to be stored on-site for potential future use
- perform spirometry with appropriate safety procedures. All spirometry tests during all visits will be performed after supervised administration of bronchodilator in the pulmonary function laboratory.
- administer the SGRQ and FPI instruments for dyspnea, fatigue and quality of life
- dispense simvastatin 20 mg with instructions regarding dosing and potential side effects
- provide a study calendar to document drug compliance. The patient should bring the completed calendar back at Visit 3.

4.3.3 Visit 3 – Day 30 (\pm 7 days)

The patient will return 30 days (\pm 7 days) after Visit 2. During this visit, the following will be performed:

- obtain a urine pregnancy test (for women of childbearing potential)
- review current medications
- review the interval medical history and conduct a physical examination
- assess for adverse events
- obtain clinical labs including: CBC, CPK, Complete Metabolic Panel, lipid panel, and sirolimus or everolimus drug level
- obtain blood for VEGF-D measurement and, if the patient has consented obtain an additional sample to be stored on-site for potential future use
- administer the SGRQ and FPI instruments for dyspnea, fatigue and quality of life
- assess for simvastatin drug compliance
- as necessary, perform simvastatin down-titration and manage drug dispensing
- provide a study calendar to document drug compliance. The patient should bring the completed calendar back at Visit 4.

4.3.4 Visit 4 – Day 60 (\pm 7 days)

The patient will return 30 days (\pm 7 days) after Visit 3. During this visit, the following will be performed:

- obtain a urine pregnancy test (for women of childbearing potential)
- review current medications
- review the interval medical history and conduct a physical examination
- assess for adverse events
- obtain clinical labs including: CBC, CPK, Complete Metabolic Panel, lipid panel, and sirolimus or everolimus drug level
- obtain blood for VEGF-D measurement and, if the patient has consented obtain an additional sample to be stored on-site for potential future use
- perform spirometry with appropriate safety procedures. All spirometry tests during all visits will be performed after supervised administration of bronchodilator in the pulmonary function laboratory.
- administer the SGRQ and FPI instruments for dyspnea, fatigue and quality of life
- assess for simvastatin drug compliance
- dispense simvastatin 40 mg (if not contraindicated) with instructions regarding dosing and a reminder regarding potential side effects
- provide a study calendar to document drug compliance. The patient should bring the completed calendar back at Visit 5.

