1.4.2 Drug Information for Simvastatin

Simvastatin is an HMG-CoA reductase inhibitor (statin) indicated as an adjunctive therapy to diet to (per package insert):

- Reduce the risk of total mortality by reducing coronary heart disease (CHD) deaths and reduce the risk of non-fatal myocardial infarction, stroke, and the need for revascularization procedures in patients at high risk of coronary events.
- Reduce elevated total-C, LDL-C, Apo B, triglycerides (TG) and increase HDL-C in patients with primary hyperlipidemia (heterozygous familial and nonfamilial) and mixed dyslipidemia.

- Reduce elevated triglycerides (TG) in patients with hypertriglyceridemia and reduce TG and VLDL-C in patients with primary dysbetalipoproteinemia.
- Reduce total-C and LDL-C in adult patients with homozygous familial hypercholesterolemia.
- Reduce elevated total-C, LDL-C, and Apo B in boys and postmenarchal girls, 10 to 17 years of age with heterozygous familial hypercholesterolemia after failing an adequate trial of diet therapy.

We will monitor patient lipids to ensure adequate levels of HDL.

Limitations of Use – Simvastatin has not been studied in Fredrickson Types I and V dyslipidemias.

The use of simvastatin is contraindicated with the administration of strong CYP3A4 inhibitors and gemfibrozil, cyclosporine, or danazol. It is also not to be used in patients with hypersensitivity to any component of this medication, active liver disease, and with elevations in hepatic transaminase levels. It is also recommended that the dose of simvastatin not exceed 10 mg daily if patients are taking verapamil, diltiazem, and dronedarone. Simvastatin should not exceed 20 mg daily if patients are taking amiodarone, amlodipine, and ranolazine. Women who are pregnant or may become pregnant or are nursing mothers should not take simvastatin. All patients should avoid grapefruit juice.

Most common adverse reactions (incidence $\geq 5.0\%$) are: upper respiratory infection, headache, abdominal pain, constipation, and nausea.

Patients should be advised of the increased risk of myopathy: rhabdomyolysis has been seen in patients taking the 80 mg dose.

Simvastatin dosing ranges from 5 mg to 40 mg once daily. The typical starting dose is 10 mg or 20 mg once a day in the evening. The recommended starting dose for patients at high risk of CHD is 40 mg/day.

2. Objectives and Specific Aims

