3.5.1 Treatment Regimen

We have chosen an intra-patient dose escalation strategy because there is no previous data from human studies to demonstrate the safety of simvastatin in combination with sirolimus or everolimus, in patients with LAM-S and LAM-TS. Dose escalation strategy will be performed only for patients who tolerate 20 mg daily simvastatin. If patients do not tolerate the 20 mg simvastatin dose, the dose will be down-titrated to 10 mg daily. If 20 mg daily is well tolerated, at visit 4 the dose will be increased to 40 mg daily for months 3 and 4. If 40 mg daily is not well tolerated, the dose will be reduced back to 20 mg daily.

Intermediate dose reductions to 15 or 30 mg/day may be undertaken if the side effect(s) is reasonably mild and tolerable.

[figure not shown]
Patients will remain on their current dose of sirolimus or everolimus without interruption, as clinically indicated.

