5.2.3 Simvastatin Dose Reduction

Any AE of \geq Grade 3 and attributed as possibly, probably or definitely related to simvastatin will result in the dose being held until the AE has resolved to \leq grade 1 or baseline, while sirolimus dosing may continue uninterrupted. If the AE resolves, reinstatement of treatment can occur but at a reduced dose as described in Table 3. If the AE recurs at the reduced dose, treatment will be held until the AE has resolved to \leq grade 1 and when resolved treatment can be reinstated at the next lower dose level. No more than 2 dose reductions are allowed during the maintenance cycles.

Table 3: Simvastatin Dose Reduction Schema

Dose mg/day	Reduce to
20 mg daily	15 mg daily
15 mg daily	10 mg daily
40 mg daily	30 mg daily
30 mg daily	20 mg daily

Toxicities that may be attributable to simvastatin include nausea, abdominal pain, diarrhea, upper respiratory infections, headache, and diarrhea. If any of these AEs occur at grade \leq 2, simvastatin may be continued and the AE managed with supportive care. For any AE with a grade \geq 3, the rules outlined in Sections 5.3 apply for holding of dose, dose reduction, removal from study and reporting requirements.

The main laboratory abnormalities which may result from simvastatin include increased CPK and liver transaminases. Patients who develop increased CPK levels ($> 2X$ ULN) will be followed with weekly CPK levels until the abnormalities return to normal. Simvastatin will be continued if CPK values are decreasing on the following week's blood sample. If persistent elevations ($> 2X$ ULN) occur over two weeks (three assessments), or symptoms such as muscle pain are present, the simvastatin study drug will be stopped. The simvastatin study drug will be stopped immediately if myositis (CPK $> 10 \times$ ULN) is documented at any time.

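### Visit 4 dispenses 40 mg without requiring the day-60 CPK and transaminases to be read, and section 5.2.3 does not say whether the increase waits for a new or falling, symptom-free CPK above 2X ULN

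*Combined protocol and SAP*

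**What the plan says.** Section 3.5.1 sets the escalation rule: "If 20 mg daily is well tolerated, at visit 4 the dose will be increased to 40 mg daily for months 3 and 4". Neither it nor section 4.1 gives a laboratory limit for tolerating the dose.

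The Visit 4 list in section 4.3.4 includes "obtain clinical labs including: CBC, CPK, Complete Metabolic Panel, lipid panel, and sirolimus or everolimus drug level" and, further down, "dispense simvastatin 40 mg (if not contraindicated) with instructions regarding dosing and a reminder regarding potential side effects". The metabolic panel includes ALT and AST (footnote to Table 1). No line links the draw to the dispensing.

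The start of 20 mg is worded differently. Section 4.3.2 opens Visit 2 with "After review of screening tests and confirmation the patient continues to meet eligibility criteria". Visit 3 (section 4.3.3) is an earlier safety check on 20 mg, with the same blood tests and the line "as necessary, perform simvastatin down-titration and manage drug dispensing".

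Section 5.2.3 governs CPK. A value above 2X ULN is repeated weekly until normal. "Simvastatin will be continued if CPK values are decreasing" a week later. If elevations above 2X ULN "occur over two weeks (three assessments), or symptoms such as muscle pain are present, the simvastatin study drug will be stopped". CPK above 10X ULN stops the drug at once. Separately, a related adverse event of Grade 3 or higher holds the dose. None of these rules mentions the increase from 20 to 40 mg.

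**The concern.** Safety is the primary objective. Section 3.5.1 explains that each patient's dose is stepped up because this combination has not been shown to be safe in these patients, so the 20 mg period should inform the decision to give 40 mg. Section 1.4.1 names muscle injury from the drug interaction as the danger, and CPK is the planned laboratory test for it.

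Followed literally, the Visit 4 list lets the dose double while that day's CPK is unread. The same holds for transaminases. Section 1.4.2 counts "active liver disease, and with elevations in hepatic transaminase levels" among the situations in which simvastatin is not to be used, but that protects a patient at day 60 only once the result is known.

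If the CPK comes back modestly raised without symptoms, section 5.2.3 gives no instruction about the increase. An increase would also blur the section's own test of whether CPK is falling, because a sample taken on 20 mg (about day 60) would be compared with one taken on 40 mg (about day 67).

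**Working it through.** The plan states no figure on this point, so the check is a comparison of texts followed by schedule arithmetic.

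**1. Is a raised day-60 CPK already covered?**

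| Day-60 CPK | Existing rule | Is the 40 mg step blocked? |
|---|---|---|
| Above 10X ULN | Stop at once (5.2.3); myopathy is a reason not to use the drug (Protocol Summary, Safety Issues) | Yes, once read |
| Above 2X ULN with muscle symptoms | Stop (5.2.3) | Yes |
| Above 2X ULN at three weekly assessments | Stop (5.2.3) | Yes, once read |
| Recorded as a related adverse event of Grade 3 or higher | Hold (5.2.3) | Yes, once read |
| Above 2X ULN, no symptoms, new or falling, none of the above | Weekly repeat; drug continued if falling | Not stated |

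Only the last row is open on the rule itself. The entries marked *once read* depend on the result being seen, which section 4.3.4 does not require before dispensing.

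**2. When can the open row arise at Visit 4?** Visit 4 falls 30 ± 7 days after Visit 3, so 23 to 37 days. A rise found at Visit 3 reaches its third weekly assessment 14 days later. That is 23 - 14 = 9 to 37 - 14 = 23 days before Visit 4, by which time CPK is no longer above 2X ULN or the drug has been stopped. What remains is a rise first seen at Visit 4, or one first seen in the 14 days before it and still raised but falling.

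**3. Exposure.** For a rise first seen at day 60, weekly assessments fall at about days 60, 67 and 74, so a stop for persistence is required about 14 days after the draw.

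- At 40 mg: 14 x 40 = 560 mg.
- At 20 mg: 14 x 20 = 280 mg.
- Difference: 280 mg at most. It is less if the rise was first seen before Visit 4, because the third assessment then comes sooner.

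Part of this may precede the result. Laboratory turnaround is not stated. Simvastatin is taken in the evening (section 3.5), so a result read the same day means 0 doses at 40 mg. A turnaround of 1 to 3 days (assumption) means 1 to 3 doses, or 20 to 60 mg above the 20 mg regimen. These doses lie inside the 14 days and are not added to them.

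**4. Frequency.** The documents give no rate for a new CPK above 2X ULN on the combination. Section 1.4.1 reports CPK of 4-10X ULN in 0.19% on simvastatin and 0.13% on placebo in large trials. With the 9 patients of section 11.1, P(at least one) = 1 - (1 - p)^9:

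- p = 0.0019 gives 1.7%.
- p = 0.0013 gives 1.2%.

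These are not per-visit rates, do not concern the combination, and leave out 2-4X ULN. They suggest a rare event and cannot be read more closely.

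**The case against.** The strongest reply is that silence is not permission. Continuing simvastatin most naturally means continuing the current dose. The increase also needs 20 mg to be well tolerated and 40 mg not to be contraindicated, and section 3.5 allows doses to be held or reduced. An investigator who has seen a raised CPK would be unlikely to double the dose. This stands as a prediction of sensible practice. It does not supply a requirement, and it does not help when the result has not been read.

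A second reply is that section 9.3.2 has laboratory results assessed under CTCAE v4.0 and lets the investigator or sponsor call any result an adverse event. A sufficiently high CPK may therefore already trigger the Grade 3 hold. This is fair and narrows the gap. The protocol does not reproduce the CTCAE cut-offs, so the upper edge of the gap cannot be fixed from it.

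A third is that the Visit 2 wording is an eligibility check on samples from an earlier visit, not a precedent for Visit 4. That also stands. It shows only that the plan states such a review elsewhere.

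A fourth is that the hazard evidence fits poorly. The rhabdomyolysis case in section 1.4.1 was a liver-transplant patient with severe muscle pain; transplant recipients are excluded here, and muscle pain with a CPK above 2X ULN already stops the drug. The case shows why muscle injury is watched for, not that a symptom-free CPK rise leads to it. Section 5.2.3 nevertheless acts on CPK without symptoms, so the plan itself treats that signal as meaningful.

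**Conclusion.** The gap is real but narrow. The day-60 results need not be read before 40 mg is dispensed, and the increase is not addressed for a new or falling, symptom-free CPK above 2X ULN that meets no stop or hold rule. The consequence is up to about 14 days at 40 mg from the day-60 draw before a stop is required, at most 280 mg more than on 20 mg. This assumes that weekly samples are counted from that draw, that the third is read promptly, and that nobody intervenes sooner.

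A reader might infer three stronger things that the documents do not support:

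- That section 5.2.3 lets the dose rise whenever CPK exceeds 2X ULN. It does not, because symptomatic, persistent and above-10X values stop the drug.
- That the unread days come on top of the 14 days. They are part of them.
- That the increase is unconditional. Tolerability and contraindication both apply; what they lack is a CPK limit and a required reading of the day-60 result.

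The case rests on a serious named hazard and a low cost of repair, not on frequency. Priority: minor to moderate safety improvement.

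**What to change.** Keep the existing contraindication condition and add two sentences.

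- To section 4.3.4: *Continue 20 mg until the day-60 CPK and transaminases have been reviewed; start 40 mg only if CPK is no more than 2X ULN and no transaminase elevation contraindicates it.*
- To section 5.2.3: *The step to 40 mg is not taken while CPK is above 2X ULN; simvastatin continues at the current dose under the weekly CPK rule.*

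The 2X ULN limit is the protocol's own trigger for weekly monitoring. Using it as a limit for escalation is a proposal for the sponsor to confirm.

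In practice, supply about a week of extra 20 mg tablets at Visit 4, release the 40 mg by telephone once the results are read, and record the release date on the case report form.

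Cost: one call per patient and about 7 tablets each, so 7 x 9 = 63 to 7 x 10 = 70 in all. A patient whose increase is held needs more tablets. For patients with acceptable results the start of 40 mg moves by about 1 to 7 days, which is 1/60 = 2% to 7/60 = 12% of the 60-day period at that dose; for the rare held patient the delay is longer. If both strengths are at home they must be clearly labelled, since a mix-up is the main new risk. No scheduled visit, blood test or patient is added.
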